4.0 Sample Size, Statistics, Selection and Withdrawal of Participants

4.1 Sample size

This study aims to recruit a total of 80 men and women, 1:1 intervention to control, to have 68 people (~15% dropout) complete the study. 34 people in each arm will provide 80% power to detect a difference of 0.468 mmol/L nocturnal glucose concentrations (SD 0.61), based on our CGM data from PREDICT 1 (unpublished data). Additionally, only 24 people are needed to provide 80% power to detect a difference of 4.2% sleep efficiency units, with SDs based on our previous sleep extension intervention (SLuMBER study) (7). These parameters are based on a significance level of 0.025, for two outcomes (calculated with *G*Power* software)

4.2 Study statistical plan

Mean differences between groups will be assessed at endpoint, adjusting for baseline values and other potential other covariates (maximum 3, as per the rule of 1 covariate per 10 participants).

For the outcomes with 3 timepoints (urinary Na, K, Na:K and calystegines), this will be assessed using a using Linear mixed models (mixed command) with change being the dependent factor, participant ID as random effect, treatment and season as fixed effects, and baseline outcome as a covariate. Variables with 2 timepoints (all other outcomes) will be assessed with an ANCOVA regression model (regress command), with baseline as a covariate. BMI, sex and age may also be covariates depending on the balancing of the arms. Sex differences will also be explored in some outcomes with known sexual dimorphisms, with the use of a sex interaction term.

A 2 -sided P value <0.05 will be considered as showing statistical significance.

Normality will be assessed visually with histogram and Q-Q plot of residuals, and heteroscedasticity with a fitted-residual plot, to satisfy the model assumptions.

We will primarily analyse outcomes on an intention-to-treat basis, analysing participants as randomised. Per-protocol analyses—restricted to participants meeting prespecified adherence criteria—will be performed to assess robustness.

All statistics will be run on Stata/MP 18.0.

[figure not shown]

Figure 5. Flow chart of the recruitment procedures

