Endpoints	
Primary
 
 • 7-day Sleep efficiency, at baseline and endline • 12-day nocturnal mean glucose (using Continuous Glucose Monitors (CGM) during sleep), at baseline (0 weeks) and endline (12 weeks) 
Secondary
 
 • Endothelium-dependent vasodilation (measured by ultrasound image analysis as Flow-Mediated Dilation (FMD)), at baseline and endline. • 12-day daytime and 24-hour glucose metabolism (CGM outcomes, glycaemic variability, time in range). • 48hrs nocturnal, daytime and stress-related heart rate variability (measure of autonomic function; higher range the more autonomic function) • 12-week daytime and night-time continuous blood pressure (Aktiia blood pressure bracelet) • Blood parameters 
 ◦ Glucose control (fasting HbA1C, fasting glucose and insulin) ◦ Lipids • Body composition 
 ◦ weight and waist circumference ◦ % body fat and lean body mass (Tanita scales) • Visual Analogue Scale (VAS) assessments of satiety, included in 4-day diet diaries. • Urinary potassium and sodium • Urinary alkaloids (calystegines) 
Compliance
 
 • Urinary potassium and sodium • Dietary assessments 
 ◦ 24-hour recall (Wk 2, 4, 8) ◦ 4-day food diary (Wk 0, 6, 12) ◦ Self-reported adherence: checklist of evening meal
Main Inclusion Criteria	Participants will be healthy male or females, aged between 40-80 years who consume ≤4 fruits and vegetables a day (excluding potatoes), with a less favourable sleep efficiency score of <85%

Statistical Methodology and Analysis	
Differences between groups (minimized for age, gender, BMI) will be analysed using Linear mixed models for outcomes with 3 timepoints (urinary outcomes, dietary intake data), with change being the dependent factor, participant ID as random effect, treatment and season as fixed effects, and baseline outcome and BMI as covariates. Variables with 2 timepoints will be assessed with an ANCOVA regression model.
 
A 2 -sided P value <0.05 will be considered as showing statistical significance.
 
For more details of statistical analysis plan, see section 4.2.

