9.6 Non-Compliance

Compliance will be monitored from several sources as outlined below:

1. 24 hr diet recalls
2. Urine sample analysis (potassium levels, as indicated by intake) (baseline, midline and endline)
3. Daily photographs of evening meals

A 24-hour dietary recall is a dietary assessment method that involves asking individuals to recall all the food and beverages they consumed in the past 24 hours. This method can be used to assess compliance with a dietary intervention by comparing the reported food intake to the prescribed dietary intake. During the 24hour dietary recall, the trained nutritionist will used a standardised protocol to assess compliance from answers. Upon finding compliance issues, this will be noted, and the nutritionist will make informed suggestions to increase access to the diet. These persons will be noted and will receive email follow ups to see if the suggestions aided adherence in the following weeks, between recalls.

The researchers will maintain a log of the non-compliances to ascertain if there are any trends developing which need to be escalated. The researcher will assess the non-compliances and action a timeframe in which they need to be dealt with.

11. Finance and Publication Policy

Source of funding

Alliance for Potato Research and Education (APRE)
[name]
[name]
Email: [contact]

Amount of funding

\$185,166 USD

Kings College London will receive and manage the funding in accordance with specification outline in the Agreement between KCL and APRE (APRE_KCL_Agreement_Revised).

The data for the study will be published in manuscript form in peer review journals and in abstract and poster format at conference proceedings/ presentations according to the research agreement between the Alliance for Potato Research and Education and Kings College London (APRE_KCL_Agreement_Revised). In brief, Kings College London will be free to publish the results of the research after providing the Alliance of Potato Research and Education with a 30-day period in which to review each publication for potentially patentable information.

Following ethical approval, the study will be registered at clinicaltrials.gov.

12. References

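### Section 4.2 promises the endpoint difference, but its mixed model for the urinary outcomes has no visit terms and estimates a midline-endline average; its list of three-timepoint outcomes also disagrees with the schedule and the synopsis

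*Combined protocol and SAP*

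**What the plan says.** Section 4.2 opens with its target: "Mean differences between groups will be assessed at endpoint", adjusted for baseline. For the outcomes that it counts as having three timepoints (urinary Na, K, Na:K and calystegines), it assigns that comparison to a linear mixed model "with change being the dependent factor, participant ID as random effect, treatment and season as fixed effects, and baseline outcome as a covariate". Neither this text nor the synopsis version includes visit or treatment by visit. Section 9.6 gives the urine schedule: "Urine sample analysis (potassium levels, as indicated by intake) (baseline, midline and endline". Each participant therefore supplies two changes from baseline.

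Everything else goes to ANCOVA: "Variables with 2 timepoints (all other outcomes) will be assessed with an ANCOVA regression model (regress command), with baseline as a covariate". Other covariates are left open: "BMI, sex and age may also be covariates depending on the balancing of the arms".

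The synopsis (section 1, Statistical Methodology and Analysis) differs. It specifies "Linear mixed models for outcomes with 3 timepoints (urinary outcomes, dietary intake data", and lists "baseline outcome and BMI as covariates". Among its secondary endpoints is "Visual Analogue Scale (VAS) assessments of satiety, included in 4-day diet diaries". The synopsis and section 3.2 place those diaries at weeks 0, 6 and 12. The study pack supplies three of them, and Table 2 ticks that row three times.

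**The concern.** A model of two post-baseline changes with one treatment coefficient cannot separate the midline effect from the endline effect. Followed literally, section 4.2 would report four urinary results as endpoint differences when they are averages over the two visits.

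The plan does not treat adherence as constant. Its compliance rule in section 3.2 tests the final four weeks separately, and the dietary recalls are used to reinforce advice. The effect could therefore fall or rise between midline and endline. Urinary potassium and sodium are listed both as secondary endpoints and as compliance measures, so the misstatement could affect two readings of the trial.

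The second issue is which model applies. An analyst following the synopsis and one following section 4.2 would handle dietary intake data and BMI differently. For satiety VAS, section 4.2 gives the week 6 values no stated use.

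**Working it through.** The plan gives no figure for these outcomes, so there is none to reproduce. The check is what the specified model estimates.

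**Inputs from the documents.** 40 per arm randomised and 34 per arm completing (section 4.1: 80 recruited, 68 completing); urine at baseline, midline and endline (section 9.6); 75% as the lowest final-four-week adherence still counted as compliant (section 3.2).

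**Assumptions, not in the documents.** Midline effect 1 and endline effect f; correlation ρ between the two changes of 0.3, 0.5 or 0.7; equal variance at the two visits; in the dropout case, all dropout after midline.

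**Step 1, expected coefficient.** Under a random intercept, a completer carries weight 1/(1+ρ) on each visit, and a participant with midline only carries weight 1 on midline. With n1 per arm at midline and n2 at endline:

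coefficient = [n2(1+f)/(1+ρ) + (n1−n2)] / [2·n2/(1+ρ) + (n1−n2)]

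With complete data this is (1+f)/2, so coefficient/endpoint effect = (1+f)/(2f).

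**Step 2, numbers.**

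| Endline relative to midline | Complete data | 40 at midline, 34 at endline per arm |
|---|---|---|
| f = 0.75 | 1.75/1.5 = 1.167 | 1.184, 1.186, 1.188 (ρ = 0.3, 0.5, 0.7) |
| f = 1 | 1.000 | 1.000 |
| f = 1/0.75 = 1.333 | 2.333/2.667 = 0.875 | about 0.86 |

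Worked case with dropout, ρ = 0.5, f = 0.75: (34 × 1.75/1.5 + 6)/(68/1.5 + 6) = 45.67/51.33 = 0.890, and 0.890/0.75 = 1.186.

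For scale only, take the 1000 mg/day of extra potassium in section 5.91 as the between-arm difference, and the 75% urinary recovery in section 3.2. Full adherence then gives 1000 × 0.75 = 750 mg/day in urine, and 75% adherence gives 562.5. The average is 656, about 94 mg/day above the endpoint value.

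**Step 3, numerical check.** In one simulated complete data set (34 per arm), the random-intercept model gave 0.5203. Separate ANCOVAs gave 0.1707 at midline and 0.8698 at endline, whose mean is the same to rounding. With season in the model and true effects of 0 and 1 SD (60 replicates), the section 4.2 model averaged 0.53. The week 12 contrast from a model with treatment by visit averaged 1.03. With effects of 1 and 1 the two agreed (1.06 and 1.07). A visit main effect alone leaves the Step 2 ratios unchanged; the interaction is what recovers the endpoint effect.

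**Step 4, precision.** SE(week 12)/SE(average):

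- Complete data: √(2/(1+ρ)) = 1.240, 1.155, 1.085 for ρ = 0.3, 0.5, 0.7.
- Dropout after midline: √{[1 − ρ²(1 − 34/40)]/34 × [68/(1+ρ) + 6]} = 1.301, 1.205, 1.120. At ρ = 0.5 this is √(0.9625/34 × 51.33) = √1.453.

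**Step 5, outcome lists side by side.**

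| Item | Synopsis | Section 4.2 |
|---|---|---|
| Urinary outcomes | Mixed model | Mixed model |
| Dietary intake data | Mixed model | Not listed with the three-timepoint outcomes |
| Satiety VAS (three diaries) | Not named in the analysis text | Two-timepoint, by default |
| BMI | Stated covariate | Optional, depending on balance |

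**The case against.** **An average is a sensible target for compliance, and it is more precise.** This stands as a reason to report the average. It does not rescue the text, because section 4.2 names the endpoint, not the average, as its target.

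**The size depends on an assumed time course.** This stands. With a constant effect there is no error, and the documents do not give the true profile.

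**Dietary data may not be an outcome in section 4.2's sense.** Table 2 labels the diary row as data for quality indices and covariates, and the synopsis lists dietary assessments under compliance. This softens the conflict but does not remove it: the synopsis names dietary intake data as a three-timepoint outcome, and section 3.3 describes diet quality among the secondary outcomes.

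**VAS by ANCOVA.** A reader might infer that sending satiety VAS to ANCOVA is invalid. The documents do not support that: week 12 ANCOVA on the first diary gives the endpoint difference that section 4.2 promises. The two-timepoint label is wrong, and the use of the middle diary is unstated. A reader might also infer that moving VAS to the mixed model is free. That is not secured. A random-intercept model with equal residual variances misstates the week 12 SE when the variances differ. In a simulation with 34 per arm it gave 0.288 against 0.327 from ANCOVA when the week 12 SD was 1.3 times the week 6 SD, and 0.287 against 0.248 in the reverse case. Under Stata's default maximum likelihood, the SE was about 5% below ANCOVA's even with equal variances (0.239 against 0.252).

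**Conclusion.** The concern holds for the urinary outcomes as specified. The model estimates a midline-endline average, weighted towards midline if endline values are missing, where section 4.2 promises the endpoint difference. Under the assumed profiles, the result is 1.17 to 1.19 times the endpoint effect if the effect falls to 75%, and 0.86 to 0.875 times if it rises from 75% to full. The disagreement between the synopsis and section 4.2 on dietary intake data and BMI, and the mislabelling of VAS, are also in the text.

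This should be corrected, but its reach is limited. A reader might infer that the primary results are compromised. They are not: sleep efficiency and nocturnal glucose are measured at baseline and endline only, and the sample size does not rest on this model.

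A reader might also infer that baseline, season and BMI use up the three-covariate limit. Section 4.2 is more naturally read as baseline plus up to three others, and it lists season as a fixed effect. Nor does the three-week recall schedule make the synopsis materially ambiguous: a model of change needs a baseline, which the diaries have and the recalls lack. The schedule section also speaks of only two recall calls.

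**What to change.** 1. In section 4.2 and the synopsis, add visit and treatment-by-visit to the mixed model, keeping baseline and season. Fit by REML with a small-sample degrees-of-freedom method, and let residual variances differ by visit. Report the week 12 treatment contrast (treatment coefficient plus its endline interaction, with midline as reference) as the endpoint estimate. If an average is wanted for compliance, report it as a second, labelled contrast.
2. Make the synopsis and section 4.2 list the same three-timepoint outcomes and treat BMI the same way.
3. Reconcile the timing of the first diary: week 0 in the synopsis and section 3.2, but week 1 of the intervention under additional measurements in the visit schedule (section 5.4). This decides whether VAS has a pre-treatment baseline. Then either keep week 12 ANCOVA for VAS, stating that it uses the first and last diaries, or use the model in item 1.
4. Date the change and disclose that midline urine is analysed within a week of collection to check compliance (section 3.2), so the change may have been made with some urinary results known. The synopsis's estimated primary completion (01/05/2025) also precedes this version (31 August 2025).

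The cost is no new data, two model terms, one contrast and a few sentences. The week 12 SE is 1.08 to 1.30 times that of the average (assumed correlation of changes 0.7 to 0.3, with and without dropout after midline).

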Daytime glycaemic control: Additionally, we plan to look at the same markers across 12-day daytime and 24-hour period.

Endothelial function: Impaired nitric oxide (NO) production causes endothelial dysfunction and increases risk of CVD (55). Capacity to synthesize NO can be assessed by ultrasound imaging of brachial arterial diameter before and after hyperaemia to determine FMD, regarded as the most reliable *in vivo* index (56). Measurements (and blood samples) will be taken at the same approximate time of day to account for circadian fluctuations, and by the same operator to reduce measurement error. All videos will be analysed using a custom MATLAB program (VidArt V13.5, [name], Department of Biomedical Engineering, Maastricht University Medical Center (MUMC)+, Maastricht, The Netherlands)

Heart rate variability (HRV) and blood pressure (BP): Improved HRV, a parameter of cardiac autonomic function, and BP are plausible health benefits of white potato consumption due to increased potassium intakes. Previous intervention studies have reported an improvement in clinic BP following potato consumption (18); however, the effects of potato intake on HRV have not been investigated to our knowledge. HRV is an indirect measure of autonomic nervous system function and predictive of risk of sudden cardiac death (57).

HRV will be measured using a small wireless heart rate/ECG monitor that continuously records interbeat intervals (eMotion Faros 180, Mega Electronics Ltd) to calculate 48-h, daytime and night-time parameters using Cardiscope Analytics software (HASIBA Medical GmbH) (58) Building on prior HRV analysis expertise (58, 59, 60), this will provide novel data on a hitherto unexplored risk factor for hypertension, T2D, chronic kidney disease and CVD events in relation to potato consumption, and will provide important mechanistic information underpinning the 3 primary outcomes. BP will be measured at home using optical blood pressure monitoring via a bracelet. 2-hour averages will be obtained continuously for 12-weeks.

Diet quality will be measured using dietary indices associated with health including PDI (61) (uPDI, hPDI), aMED (62), aHEI (62) and HFD (63, 64) to demonstrate the impact of potatoes on overall diet quality and for inclusion as a covariate in analysis.

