5.4 Randomisation Procedures

Participants will be randomised to either the intervention or control arm, with an allocation ratio of 1:1. A minimisation procedure will be used that considers gender, age, ethnicity, BMI) in the randomization, by using the Shiny App software, which can be accessed at:

https://fsella.shinyapps.io/VM_app/?_ga=2.186170153.125318758.1628174827-961835063.1626383516 (71).

Screening data will be entered into minimisation software, by the research lead (See randomisation SOP). This database will balance the treatment arms for the following variables:

1. *Gender*. 2 groups: Male; Female
2. *Age*. 2 groups: 40-59; 60-80 y
3. *BMI*. 2 groups: Healthy weight 18.5-24.9; Overweight-Obese ≥ 25

Randomisation codes will be generated by the software and recorded on the relevant documentation in the Case Report Form and enrolment log. The randomization protocol follows the same protocol as used previously by our group for a parallel, two-arm, randomized controlled trial (30) for which a study statistician was employed. It has not been deemed necessary to employ a study statistician on the current trial due to the similarity of the study design, but the protocol will be discussed with a statistician from the King's Joint Clinical Trials Unit.

Participants will be blinded to whether they are receiving the intervention or the control, but it is not possible to blind them to the food itself. Also, as the study team is limited by resources, observer blinding is also impossible; however, the researcher undertaking statistical analysis will be blinded prior to analysis using a second set of study ID codes. FMD analysis will be conducted through semi-automated software analyses, which will reduce bias.

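### The primary ANCOVA leaves the minimisation factors to an undefined balance check instead of fixing them in the model

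*Combined protocol and SAP*

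**What the plan says.** **Allocation.** Section 5.4 (Randomisation Procedures) specifies 1:1 minimisation. "This database will balance the treatment arms for the following variables" introduces a list of three factors: gender (two groups), age (40-59, 60-80) and BMI (18.5-24.9, 25 and over). The synopsis names the same three. The narrative sentence above the list adds a fourth: "A minimisation procedure will be used that considers gender, age, ethnicity, BMI) in the randomization".

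**Analysis.** Both primary outcomes, sleep efficiency and mean nocturnal glucose, are measured at baseline and endline. They therefore fall under this rule in section 4.2: "Variables with 2 timepoints (all other outcomes) will be assessed with an ANCOVA regression model (regress command), with baseline as a covariate". The next sentence reads: "BMI, sex and age may also be covariates depending on the balancing of the arms". The section opens with a general limit: "adjusting for baseline values and other potential other covariates (maximum 3, as per the rule of 1 covariate per 10 participants".

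**Other covariates.** Section 3.3 proposes diet-quality indices "to demonstrate the impact of potatoes on overall diet quality and for inclusion as a covariate in analysis", without saying which analyses. The synopsis fixes BMI as a covariate only in the mixed models for outcomes with three timepoints, which do not include the primaries. Nothing else in the documents fixes the ANCOVA covariates.

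**The concern.** The reason to adjust for allocation factors is that they may be prognostic, not that they happen to be unbalanced. Minimisation makes imbalance on its own factors unlikely, so a balance trigger will usually leave them out. If they predict outcome beyond its baseline value, their variance then stays in the error term although allocation has removed most of it from the treatment contrast. The standard error is overstated and the test is conservative. Omission by itself causes no bias and no type I inflation, and nothing is lost if the factors are not prognostic.

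The second point is that the primary model is not fixed. With no criterion, coding or decision time, two analysts could fit different models from the same plan. The limit of three extra covariates does not reserve places for the minimisation factors, and diet quality is a further candidate.

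**Working it through.** **1. The plan's own sample size.** Section 4.1 gives a difference of 0.468 mmol/L, SD 0.61, alpha 0.025 and 80% power.

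- Standardised effect: 0.468/0.61 = 0.767.
- Normal approximation: n per arm = 2(2.241 + 0.842)²/0.767² = 32.3, so 33.
- Noncentral t: 33 per arm gives 79.2% power and 34 gives 80.5%.
- Dropout: 68/0.85 = 80.

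The stated 34 per arm and 80 recruited reproduce, so the concern does not rest on a wrong figure.

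**2. Mechanism.** Let the factors explain a share R² of the variance left after baseline. If they were perfectly balanced, the true standard error of the contrast would shrink by √(1 − R²), but a baseline-only model would not see it. The reported standard error would be too wide by 1/√(1 − R²): 1.026, 1.054, 1.118 and 1.195 for R² of 0.05, 0.10, 0.20 and 0.30. Real minimisation with dropout balances less than perfectly, so the actual figures should be lower.

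**3. Simulation.** These inputs are assumptions, not in the documents:

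- baseline correlation 0.5;
- R² from 0 to 0.30;
- biased-coin marginal minimisation on the three grouped factors, with favoured-arm probability 0.8, 0.9 or 1.0 (section 5.4 names an app but no assignment rule);
- age uniform on 40-80, BMI normal(26, 4) truncated to 18.5-35, sex split 60/40;
- factor effects either grouped or continuous.

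In each trial 80 are allocated, 12 are lost at random and 68 are analysed, with 10,000 trials per cell. Ranges are over the six settings.

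| R² | Baseline-only SE, reported/true | Type I at 0.025 | Type I at 0.05 |
|---|---|---|---|
| 0 | 0.986-1.004 | 0.025-0.028 | 0.049-0.052 |
| 0.05 | 1.007-1.018 | 0.022-0.025 | 0.045-0.049 |
| 0.10 | 1.024-1.033 | 0.020-0.022 | 0.039-0.044 |
| 0.20 | 1.060-1.099 | 0.012-0.018 | 0.029-0.037 |
| 0.30 | 1.100-1.164 | 0.010-0.013 | 0.025-0.032 |

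With the factors always in the model, the standard-error ratio stays at 0.985-1.018. Both alphas are shown because section 4.1 uses 0.025 and section 4.2 uses 0.05.

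**4. Power for nocturnal glucose.** If 0.61 is the unadjusted SD, the post-baseline SD is 0.61 × √(1 − 0.5²) = 0.528 and the effect is 0.468/0.528 = 0.886 SD. The last two columns compare always adjusting with adjusting only on a trigger (p<0.05, or a difference above 0.25 SD).

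| R² | Baseline only, 0.025 | Adjusted, 0.025 | Change vs trigger, 0.025 (points) | Change vs trigger, 0.05 (points) |
|---|---|---|---|---|
| 0 | 0.903-0.910 | 0.896-0.902 | -0.8 to -0.1 | -0.6 to -0.1 |
| 0.05 | 0.906-0.913 | 0.908-0.917 | 0.0 to 1.0 | -0.1 to 0.5 |
| 0.10 | 0.911-0.917 | 0.921-0.929 | 0.8 to 1.6 | 0.3 to 1.1 |
| 0.20 | 0.916-0.924 | 0.943-0.955 | 1.8 to 3.7 | 0.9 to 2.2 |
| 0.30 | 0.924-0.939 | 0.960-0.976 | 2.2 to 5.1 | 1.1 to 2.6 |

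If 0.61 were already a post-baseline residual SD, which section 4.1 does not say, the changes at 0.025 would be -0.8 to -0.2, 0.4 to 1.1, 1.4 to 3.0, 3.0 to 6.8 and 5.1 to 10.1 points.

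**5. Power for sleep efficiency.** Section 4.1 says "only 24 people are needed to provide 80% power to detect a difference of 4.2% sleep efficiency units", without saying whether 24 is a total or per arm.

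- As a total (12 per arm), the implied effect is 1.336 SD (SD 4.2/1.336 = 3.14), and 34 per arm gives 99.9% power.
- As a per-arm number, the implied effect is 0.915 SD (SD 4.59), and 34 per arm gives 92.8% at 0.025 and 96.1% at 0.05. With baseline correlation 0.5 these become 97.9% and 99.0%.

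So at most about two points remain to be gained there with that correlation.

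**6. How often a trigger would fire.** The figures are for any factor among 68 completers.

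| Rule | p<0.05 | Over 0.25 SD |
|---|---|---|
| Minimised on groups | about 1% or less | 4-11% (grouped), 23-28% (continuous) |
| Balanced on continuous values | under 1% | 20-24% (grouped), 4-8% (continuous) |
| No minimisation | 13-14% | 65-66% |

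**7. Cost of adjusting.** Residual degrees of freedom fall from 68 − 3 = 65 to 68 − 6 = 62.

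**The case against.** The strongest objection is that the consequence is small. Up to R² = 0.10 the power change is about -1 to +2 points at 0.025, on a base of about 90-92%, and the documents do not show that the factors are prognostic at all. A conservative test does not undermine a positive result. The larger gains need either R² of 0.20 to 0.30 or 0.61 read as a residual SD. The second reading is less natural, since section 4.1 takes the SD from cohort CGM data and mentions no baseline adjustment. All of this stands and limits the weight of the point, but it does not make the balance trigger a sound rule.

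A second objection is that the analyst will be blinded by recoded IDs (section 5.4), so the open choice is harmless. This stands only in part. A two-arm p-value does not depend on which arm is which, so recoding hides direction but not significance. In the worst case, picking the most favourable of the eight covariate sets gave a type I error of 0.030-0.033 at nominal 0.025, in a run with binary factors. Blinding makes that unlikely but supplies no criterion.

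Third, the limit of three can be read as applying to covariates other than baseline, and section 4.2 then names exactly three. That is the natural reading. It is still not stated, and the diet-quality proposal in section 3.3 leaves the places open.

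**Conclusion.** The concern holds. The primary ANCOVA is not fully specified, and its rule for the minimisation factors is the wrong one: it will usually drop them, and it ignores whether they are prognostic. The statistical loss is conditional and modest. At the planned glucose effect, always adjusting is worth about 0-2 points of power at alpha 0.025 for R² of 0.05 to 0.10, and 2-5 points for 0.20 to 0.30. The gain is smaller at 0.05, and at most about two points for sleep efficiency with the assumed baseline correlation. Omitting the factors threatens neither unbiasedness nor type I control. These sizes rest on the assumed prognostic strength, baseline correlation and minimisation rule. The need to fix the model in advance does not depend on them. The point should be corrected because the remedy is cheap and makes the primary model reproducible.

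**What to change.** Replace the conditional sentence in section 4.2 with: *The primary ANCOVA for each outcome includes treatment, the baseline value, sex, age and BMI (the minimisation factors), whatever the observed balance.* In addition:

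- State whether age and BMI enter as the minimisation groups or as continuous values. At R² = 0.20 the gain over baseline-only is similar: 2.6-3.7 points grouped and 2.2-3.7 continuous.
- State that the limit of three excludes the baseline value and that these three factors fill it in the primary model, so that diet quality does not displace them. One covariate per ten among 68 completers would allow six, so four terms fit.
- Reconcile the mention of ethnicity in section 5.4 with the numbered list and the synopsis, which omit it. If it was not used, deleting the word is enough. If it was, it belongs in the model, the limit must rise, and the cost exceeds the three degrees of freedom counted here.
- Date the change and make it before any outcome is analysed by arm. The document is dated 31 August 2025 and the synopsis estimated primary completion for 01/05/2025, so data collection may already be over.

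The cost is SAP wording, three residual degrees of freedom, and up to about one point of power if the factors are not prognostic.
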